6.1.3.1 Model checking procedures

All patients with available data after baseline and until Week 12 will be included in the interim and in the primary analyses. If study drug is permanently discontinued before Week 12, data collected after permanent discontinuation will not be considered for the purpose of the primary analyses. The primary variable analysis model is known to give unbiased results under the assumption that missing data are at random (MAR), i.e. given observed data the missingness does not depend on unobserved data. In the event that many patients discontinue treatment, alternative estimands considering the effect of LYS006 versus placebo may also be investigated.

6.1.3.2 Graphical presentation of results

Model-based geometric mean treatment estimates (+/- SE) as well as model-based geometric mean treatment ratio estimates (+/- SE) will be plotted over time and by treatment. The baseline value will also be presented in the model-based geometric mean treatment estimates (+/- SE) graphs for better visualization purposes. The baseline value that will be displayed is the averaged baseline value across treatments.

6.1.4 Sensitivity analyses

Commercially Confidential Information

6.1.5 Supportive analyses

In order to have better understanding of the treatment effect, the absolute change from baseline and the percentage change from baseline in total inflammatory facial lesion count will also be explored using a Bayesian mixed effect model for repeated measures (MMRM) using Proc MCMC in SAS software ([Chen 2011](#)). Baseline inflammatory facial lesion count will be included in the model as a continuous covariate. The model will also include treatment group, visit, treatment group by visit interaction, baseline inflammatory facial lesion count

Commercially Confidential Information as fixed effects. Non-informative priors will be utilized for the fixed effects and for the covariance coming from a normal distribution and an inverse Wishart distribution, respectively. An unstructured covariance will be assumed; other covariance structures will be investigated if there is a convergence issue. The baseline inflammatory facial lesion count will be centered and standardized prior to being included in the model.

The posterior estimates of the treatment effect and the treatment difference (along with its 90% credible interval) at each post baseline visit (with Week 12 being of primary interest) will be provided. The results of the treatment effects will be presented as arithmetic means and the results of the treatment comparison to placebo will be reported in terms of difference of the arithmetic means.

The Bayesian posterior probability for statistical significance, i.e., the probability that the treatment effect of LYS006 is better than placebo, $\text{Prob}(\text{LYS006} - \text{placebo} < 0)$, will be obtained.

As an additional supportive analysis, the same Bayesian MMRM as for the primary analysis will be fitted and appropriate contrasts will be estimated in order to compare LYS006 high dose group versus placebo group on the average treatment effect combining week 8 and week 12 data.

6.1.5.1 Model checking procedures

All patients with available data after baseline and until Week 12 will be included in the interim and in the above supportive analyses. If study drug is permanently discontinued before Week 12, data collected after permanent discontinuation will not be considered for the purpose of the above supportive analyses.

6.1.5.2 Graphical presentation of results

Model-based arithmetic mean treatment estimates (+/- SE) as well as model-based arithmetic mean treatment difference estimates (+/- SE) will be plotted over time and by treatment. Baseline will also be presented as 0 in these model-based plots for better visualization of the absolute and percent changes from baseline over time.

Posterior density plots for the treatment effect will also be obtained.

As additional supportive analyses, other factors such as gender, race, center, assessor and approach of the assessment (digital or clinic) may also be considered in the primary analysis model and the above supportive analysis models either as a fixed effect or as a sub-group analyses variable to investigate for potential heterogeneity. If heterogeneity is observed, then this method may be applied to other investigated PD endpoints.

Further, supportive analyses may be performed adding other covariates in the models such as baseline IGA and other baseline characteristics.

6.2 Exploratory objectives

Commercially Confidential Information

Commercially Confidential Information

6.2.1 Variables

Commercially Confidential Information

Commercially Confidential Information

6.2.2 Descriptive analyses

Commercially Confidential Information

Commercially Confidential Information

6.2.3 Statistical model, assumptions and hypotheses

Commercially Confidential Information

Commercially Confidential Information

6.2.4 Graphical presentation of results

Commercially Confidential Information

7 Statistical methods for safety and tolerability data

All subjects within the Safety analysis set will be included in the safety data analysis.

7.1 Variables

The safety and tolerability variables are the number and severity of AEs/SAEs, vital signs (body temperature, height, weight, blood pressure and pulse rate), ECG intervals (PR interval, QRS duration, heart rate, RR, QT and QTcF), laboratory measurements (hematology, clinical chemistry, urinalysis), as well as subject demographics, baseline characteristics, and treatment information.

7.2 Descriptive analyses

Subject demographics and other baseline characteristics

All data for background and demographic variables will be listed by treatment group and subject. Summary statistics will be provided by treatment group. Subject demographics will include age, sex, race, ethnicity, country, height, weight and BMI. Baseline disease characteristics include but are not limited to: facial inflammatory lesion counts (papules, pustules, nodules),

Commercially Confidential Information

Relevant medical history, current medical conditions, results of laboratory screens, drug tests and any other relevant information will be listed by treatment group and subject.

Protocol deviations

In addition to the pre-defined standard protocol deviation terms, Novartis has defined 6 new protocol deviations and the corresponding relationship (health status related vs. site lockdown, subject concerns, etc.) to the COVID-19 pandemic in line with “Guidance on Conduct of Clinical Trials of Medical Products during the COVID-19 Public Health Emergency” (January 2021) from FDA and “Guidance on the Management of Clinical Trials during the COVID-19 (Coronavirus) Pandemic” (February 2021) from EMA as listed below.

- Missing visits
- Changes in procedures and assessments
- Planned visits not done at sites
- Changes in drug supply method
- Treatment not given
- Subject discontinuation due to COVID-19 situation

A summary table for the pandemic related/not pandemic related protocol deviations by category and relationship (and in total) will be provided by treatment group for all subjects randomized. For those related to the pandemic, “all COVID-19 pandemic related” protocol deviations will be summarized together and by specific type of reason (site issue, subject’s infection, etc.). The percentages will be calculated out of total randomized patients, since the intent is to show how much the pandemic related deviations impacted the study as a whole.

All protocol deviations will be listed. A separate listing will be provided for COVID-19 related protocol deviations.

Treatment

Data for study drug administration and concomitant therapies will be listed by treatment group and subject.

Duration of exposure to study drug in days, as well as actual total doses, actual dose intensities (total amount of drug administered per unit of time), and relative dose intensities (ratio of actual dose intensity to planned dose intensity) will be summarized using descriptive statistics by treatment group for the safety analysis set.

Compliance to the study treatment will be assessed by the frequency of dose interruptions and percent of days with received planned dose by treatment group for the safety analysis set.

Compliance to the study treatment in the percent of capsules taken will be summarized by visit and overall, and also listed.

Reason for dose interruption will be listed by subject and summarized.

Concomitant therapies prior to and after the start of study treatment will be listed and summarized by treatment group for the safety analysis set.

Vital signs

All vital signs data will be listed by treatment group, subject, and visit/time and if ranges are available abnormalities (and relevant orthostatic changes) will be flagged. Summary statistics will be provided by treatment group and visit/time.

ECG evaluations

All ECG data will be listed by treatment group, subject and visit/time, abnormalities will be flagged. Summary statistics will be provided by treatment group and visit/time.

Clinical laboratory evaluations

All laboratory data will be listed by treatment group, subject, and visit/time and if normal ranges are available abnormalities will be flagged. A separate listing will be provided presenting all parameters in a subject with any abnormal values. Summary statistics will be provided by treatment group and visit/time.

The laboratory data will be graded by the low/normal/high classifications based on laboratory normal ranges.

The following by-treatment summaries will be generated separately for hematology, biochemistry and urinary laboratory tests:

- Shift tables using the low/normal/high/(low and high) classification to compare baseline to the worst on-treatment value.
- Listing of all laboratory data with values flagged to show the classifications relative to the laboratory normal ranges.

Adverse events

All information obtained on adverse events will be displayed by treatment group and subject.

Summary tables for AEs will include only AEs that started or worsened after first dose, the *treatment-emergent* AEs (TEAEs). However, all safety data (including those from the pre and post-treatment periods) will be listed and those collected during the pre-treatment and post-treatment period are to be flagged. Listings of all AEs will be provided.

The incidence of TEAEs (new or worsening after first dose) will be summarized by system organ class (SOC) and/or preferred term (PT), maximum severity and by treatment.

Deaths reportable as SAEs and non-fatal SAEs will be listed by subject and tabulated by type of AE and treatment.

SAEs, non-serious AEs, AEs leading to study drug discontinuation, drug-related AEs CCI events will be tabulated.

A subject with multiple AEs within a body system is only counted once towards the total of this body system and treatment.

Adverse event reporting for Clinical Trial Safety Disclosure (CTSD)

For the legal requirements of ClinicalTrials.gov and EudraCT, two required tables, 1) on treatment-emergent adverse events which are not serious adverse events with an incidence greater than X% and 2) on treatment-emergent serious adverse events and SAE suspected to be related to study treatment, will be provided by SOC and PT on the safety analysis set population. These tables will be produced by Novartis. The value of the cutoff value X will be decided with the team when disclosure tables are prepared.

The summary will be done by treatment i.e. active (LYS006) or Placebo, regardless of the dose level.

If for a same patient, several consecutive AEs (irrespective of study treatment causality, seriousness and severity) occurred with the same SOC and PT:

- a single occurrence will be counted if there is \leq 1-day gap between the end date of the preceding AE and the start date of the consecutive AE
- more than one occurrence will be counted if there is $>$ 1-day gap between the end date of the preceding AE and the start date of the consecutive AE.

For occurrence, the presence of at least one SAE / SAE suspected to be related to study treatment / non-SAE has to be checked in a block e.g., among AE's in a \leq 1-day gap block, if at least one SAE is occurring, then one occurrence is calculated for that SAE.

The number of deaths resulting from SAEs suspected to be related to study treatment and SAEs irrespective of study treatment relationship will be provided by SOC and PT.

Other safety evaluations

Commercially Confidential Information

All other safety evaluations (e.g. pregnancy test results for women) will be listed by treatment group, subject and visit/time.

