9.1 Adverse events

An adverse event (AE) is any untoward medical occurrence (i.e., any unfavorable and unintended sign [including abnormal laboratory findings], symptom or disease) in a subject after *providing written informed consent* for participation in the study until the end of study visit. Therefore, an AE may or may not be temporally or causally associated with the use of a medicinal (investigational) product.

In addition, all reports of intentional misuse and abuse of the study treatment are also considered an adverse event irrespective if a clinical event has occurred. See Section 9.6 for an overview of the reporting requirements.

The occurrence of adverse events must be sought by non-directive questioning of the subject at each visit during the study. Adverse events also may be detected when they are volunteered by the subject during or between visits or through physical examination finding, laboratory test finding, or other assessments.

Abnormal laboratory values or test results constitute adverse events only if they fulfill at least one of the following criteria:

- they induce clinical signs or symptoms,
- they are considered clinically significant,
- they require therapy.

Clinically significant abnormal laboratory values or test results should be identified through a review of values outside of normal ranges/clinically notable ranges, significant changes from baseline or the previous visit, or values which are considered to be non-typical in patients with underlying disease. Investigators have the responsibility for managing the safety of individual subject and identifying adverse events. Alert ranges for liver and kidney related events are included in Appendix 1 and Appendix 2, respectively.

Adverse events should be recorded on the Adverse Events CRF under the signs, symptoms or diagnosis associated with them, and accompanied by the following information:

1. The Common Toxicity Criteria (CTC) for AE grade (version 4.0 or higher). A copy of the CTCAE grading will be provided separately.

If CTCAE grading does not exist for an adverse event, use:

1=mild,

2=moderate,

3=severe

4=life threatening* (see Section 9.2 for definition of a serious adverse event (SAE))

*Note: There may be cases where a CTCAE with a grade of 4 (life-threatening) may not necessarily be an SAE (e.g. certain laboratory abnormalities in the absence of meeting other seriousness criteria).

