11.5 Analysis of secondary variable(s)

11.5.1 Safety

For all safety analyses, the safety analysis set will be used if not otherwise specified. All listings and tables will be presented by treatment group.

Vital signs

All vital signs data will be listed by treatment group, subject, and visit/time and if ranges are available abnormalities (and relevant orthostatic changes) will be flagged. Summary statistics will be provided by treatment and visit/time.

ECG evaluations

All ECG data will be listed by treatment group, subject and visit/time, abnormalities will be flagged. Summary statistics will be provided by treatment and visit/time.

Clinical laboratory evaluations

For laboratory tests covered by the CTCAE version 4.0 or higher, the laboratory data will be graded accordingly. The calculation of CTCAE grades will be based on the observed laboratory values only, clinical assessments will not be taken into account. For laboratory tests covered by CTCAE, a Grade 0 will be assigned for all non-missing values not graded as 1 or higher. Grade 5 will not be used.

For laboratory tests where grades are not defined by CTCAE, results will be graded by the low/normal/high classifications based on laboratory normal ranges.

The following by-treatment summaries will be generated separately for hematology, biochemistry and urinary laboratory tests:

- frequency table for newly occurring on-treatment grades 3 or 4
- shift tables using CTCAE grades to compare baseline to the worst on-treatment value
- for laboratory tests where CTCAE grades are not defined, shift tables using the low/normal/high/(low and high) classification to compare baseline to the worst on-treatment value.
- listing of all laboratory data with values flagged to show the corresponding CTCAE grades and the classifications relative to the laboratory normal ranges.

Adverse events (AEs)

All information obtained on AEs will be displayed by treatment group and subject.

Summary tables for AEs include only AEs that started or worsened after first dose, the *treatment-emergent* AEs (TEAEs). However, all safety data (including those from the pre and post-treatment periods) will be listed and those collected during the pre-treatment and post-treatment period are to be flagged. Listings of all AEs will be provided.

The incidence of TEAEs (new or worsening after first dose) will be summarized by system organ class or preferred term, severity and by treatment group.

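### SAP 7.2 drops the protocol's CTCAE grading of laboratory data, and with it the by-arm table of new grade 3 or 4 values and the grade shift tables

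*SAP*

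**What the plan says.** Protocol 11.5.1 (Safety, clinical laboratory evaluations) sets a two-part rule. For tests with CTCAE criteria: "For laboratory tests covered by the CTCAE version 4.0 or higher, the laboratory data will be graded accordingly". The grading is meant to be objective: "The calculation of CTCAE grades will be based on the observed laboratory values only, clinical assessments will not be taken into account". Grade 0 goes to any non-missing value that does not reach Grade 1, and Grade 5 is not used. Low/normal/high is the fallback for tests without a CTCAE grade. The section then names four outputs, produced separately for hematology, biochemistry and urinary tests:

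- a "frequency table for newly occurring on-treatment grades 3 or 4"
- "shift tables using CTCAE grades to compare baseline to the worst on-treatment value"
- low/normal/high shift tables, restricted to tests without CTCAE grades
- a listing of all data with "values flagged to show the corresponding CTCAE grades" as well as the normal-range class.

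SAP 7.2 (Descriptive analyses, clinical laboratory evaluations) has a single rule without that restriction: "The laboratory data will be graded by the low/normal/high classifications based on laboratory normal ranges". Under an equivalent lead-in it names two outputs: "Shift tables using the low/normal/high/(low and high) classification to compare baseline to the worst on-treatment value", and a listing flagged by normal range only. Ahead of these it also plans a separate listing of all parameters for any subject with an abnormal value, and summary statistics by treatment group and visit. SAP 7.3 adds boxplots, and mean and individual figures for selected parameters. SAP 1.1 describes the document as implementing the analysis planned in the protocol.

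**The concern.** The SAP keeps the protocol's fallback rule, removes its restriction to tests without CTCAE grades, and so applies it to every laboratory test. This is a stated rule that conflicts with the protocol, rather than a detail left open. Protocol 11.5.1 leaves no choice about laboratory grading to the SAP.

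Two kinds of information are lost from the tables. First, a normal-range class does not separate a slight excursion from a severe one, so new severe abnormalities are no longer counted by arm. Second, worsening within an abnormal class cannot be seen: a patient slightly high at baseline and severely high on treatment is tabulated as high to high.

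Safety and tolerability is the trial's only secondary objective, and SAP 7.1 names laboratory measurements among the safety variables. Protocol 3.7 warns of unknown and possibly serious risks at this stage of development, and Protocol 10.4 states that no independent data monitoring committee will be set up. An objective summary of severe laboratory change is therefore worth keeping.

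**Working it through.** The plan states no figure on this point, so the check is a comparison of the two laboratory subsections.

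| Item | Protocol 11.5.1 | SAP 7.2 |
|---|---|---|
| Grading rule | CTCAE where covered, otherwise low/normal/high | low/normal/high for all tests |
| New on-treatment grade 3 or 4, frequency by treatment | planned | absent |
| CTCAE shift tables, baseline to worst value | planned | absent |
| Low/normal/high shift tables | only tests without CTCAE grades | all tests |
| Listing | CTCAE grade and range class | range class only |

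**Count of outputs.** The protocol names 4 and the matching SAP list names 2, so 4 − 2 = 2 are absent. Of the 2 that remain, 1 (the listing) loses its CTCAE flag and 1 (the low/normal/high shift table) is widened. The count covers only the items under the matching lead-in in each document. The SAP's extra listing, by-visit statistics and figures stand outside it, and none of them uses grades.

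**Resolution lost.** For a covered test the protocol has Grades 0, 1, 2, 3 and 4, which is 5 levels. Grades 1 to 4 in one direction can all fall into a single SAP class, so up to 4 abnormal grades merge. This is a ceiling, because the documents do not list which tests CTCAE covers or how many grades each has. The two scales are also not nested. A value outside the normal range that does not reach Grade 1 is Grade 0, and low/normal/high keeps direction, which a grade alone does not.

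**Do the adverse event tables fill the gap?** SAP 7.2 tabulates treatment-emergent events by maximum severity. Protocol 9.1 limits which laboratory values become events: "Abnormal laboratory values or test results constitute adverse events only if they fulfill at least one of the following criteria". The criteria are signs or symptoms, clinical significance, or need for therapy. A value can therefore be Grade 3 or 4 on its number alone without being an adverse event. Protocol 11.5.1 grades from the observed value and leaves clinical assessment out, so the two summaries answer different questions.

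**Could redaction explain the difference?** The SAP laboratory subsection runs without a redaction mark from its heading to the adverse events subsection. The visible SAP text nowhere mentions CTCAE and gives no reason for the change.

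**The case against.** The strongest reply is that little is lost in practice. The trial is a non-confirmatory proof of concept with 56 patients (24, 8 and 24). Every laboratory value is listed by arm, subject and visit, and the SAP adds a listing for subjects with any abnormal value, by-visit statistics and figures that the protocol's laboratory subsection does not name. At this size a reader can find extreme values by inspection. Protocol 8.6.4 has clinically relevant deviations discussed with the sponsor and assessed as possible adverse events. The stated secondary endpoint is the number and severity of adverse events, not laboratory grade. Parts of both documents' other safety evaluations are redacted, as are the protocol's events of special interest, so threshold-based tables for particular organs could exist there. Grades could also be derived later from the stored values.

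Much of this stands, and it limits the weight of the point. The endpoint is intact, no efficacy decision changes, and severe values are not hidden. None of it removes the conflict, however. Listings and plots do not supply the by-arm count of new grade 3 or 4 values or the grade shifts that the protocol specifies. Redacted text elsewhere might give a reason, but SAP 7.2 would still state a rule that contradicts Protocol 11.5.1. Grades derived after unblinding would be a post hoc addition instead of the planned summary.

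**Conclusion.** The concern holds. SAP 7.2 replaces the protocol's CTCAE grading with low/normal/high for all tests, omits two of the four planned laboratory outputs and removes the CTCAE flag from a third, with no visible explanation. The consequence is confined to descriptive laboratory safety reporting, so this should be corrected but does not threaten the primary analysis or the adverse event endpoint. The number of patients affected cannot be calculated from the documents. The conclusion rests on the visible text: the mismatch between the two subsections is certain, while redacted sections cannot be checked for a justification or a partial substitute.

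**What to change.** Amend the laboratory part of SAP 7.2. For tests covered by CTCAE, restore:

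- grading from observed values, with the protocol's Grade 0 and Grade 5 conventions
- the by-arm frequency table of newly occurring on-treatment grade 3 or 4 values
- shift tables from baseline grade to worst on-treatment grade
- the CTCAE grade flag in the listing.

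Keep low/normal/high for tests without CTCAE grades. The SAP's additional listing, by-visit summaries and figures can stay. If the simplification was deliberate, state it in the SAP as a change from the protocol, with the reason, before database lock.

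The cost is a short SAP amendment and the programming of a few tables. The laboratory values are already collected, so no site procedure or data capture changes.

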1.4 Study purpose

The study is designed to assess clinical efficacy and safety of LYS006 in adult patients with moderate to severe inflammatory acne as well as exploring dose relationship. This information will support the decision to initiate a dose ranging study in inflammatory acne and guide dose selection for that planned study.

2 Objectives and endpoints

2.1 **Primary objective(s)**

Baseline-adjusted total inflammatory facial lesion count at Week 12

Secondary objective(s)	Endpoints related to secondary objective(s)	
• To assess the safety and tolerability of LYS006 in patients with moderate to severe inflammatory acne	• Number and severity of AEs	

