1.4 Study design and treatment

This is a randomized, placebo-controlled, subject and investigator blinded, multicenter, non-confirmatory, parallel-group, proof-of-concept study in adult patients with moderate to severe facial inflammatory acne. After an initial screening period (up to 4 weeks), the study will be conducted over a treatment period of 12 weeks to evaluate the clinical efficacy of LYS006 versus placebo. Fifty-six (56) patients will be randomized in a 3:1:3 ratio to one of the following treatment groups:

- Group 1: LYS006 capsules, high dose CCI N=24
- Group 2: LYS006 capsules, low dose CCI N=8
- Group 3: LYS006 placebo CCI , N=24

Commercially Confidential Information

Exposure to placebo will be limited to a maximum of 12 weeks.

After treatment period completion, all patients will enter a post-treatment safety follow-up period of 4 weeks without study drug administration.

The maximum duration of study participation will be 20 weeks.

Commercially Confidential Information

2 First interpretable results (FIR)

Commercially Confidential Information

Commercially Confidential Information

Commercially Confidential Information

Commercially Confidential Information

Commercially Confidential Information

3 Interim analyses

Commercially Confidential Information

4 Statistical methods: Analysis sets

For all analysis sets, subjects will be analyzed according to the study treatment(s) received. This implies that for subjects for whom the actual treatment received does not match the randomized treatment, the treatment actually received will be used for the analysis.

The Safety analysis set will include all subjects that received at least one dose of study drug.

Commercially Confidential Information

The PD analysis set will include all subjects with available PD data, who received any study drug and with no protocol deviations with relevant impact on PD data.

The analysis sets and protocol deviation codes are related as follows:

Table 4-1 Protocol deviation codes and analysis sets

Category Deviation code	Text description of deviation	Data exclusion
Subjects are excluded from all (safety) analysis in case of these protocol deviations:		Exclude subject completely from all (safety) analysis sets
INCL01	Deviation from inclusion criterion 1 (Written informed consent must be obtained before any assessment is performed)	Yes

Commercially Confidential Information

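### The two registry adverse-event tables pool the high and low LYS006 doses, against the protocol's by-group rule, so they lose dose attribution and may omit some non-serious events

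*SAP*

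**What the plan says.** Protocol 11.5.1 introduces the safety analyses with a general rule: "All listings and tables will be presented by treatment group". It repeats by-group presentation for the incidence of treatment-emergent events and makes no exception for disclosure outputs. The groups are those of SAP 1.4: "Fifty-six (56) patients will be randomized in a 3:1:3 ratio to one of the following treatment groups", namely "Group 1: LYS006 capsules, high dose CCI N=24", "Group 2: LYS006 capsules, low dose CCI N=8" and "Group 3: LYS006 placebo CCI , N=24".

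Under its heading on Clinical Trial Safety Disclosure, SAP 7.2 defines two tables on the safety analysis set. One covers non-serious treatment-emergent events with incidence above X%. The other covers serious treatment-emergent events and those suspected to be related to treatment. For both, "The summary will be done by treatment i.e. active (LYS006) or Placebo, regardless of the dose level". On the cutoff, the SAP says: "The value of the cutoff value X will be decided with the team when disclosure tables are prepared".

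Earlier in SAP 7.2, the general adverse-event paragraph keeps the display of all adverse-event information by treatment group and subject.

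**The concern.** The SAP rule and the protocol rule cannot both hold for these two tables, and the SAP text that can be read does not present the pooling as a departure or justify it.

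The study purpose in Protocol 1.4 is to assess efficacy and safety "as well as exploring dose relationship", in support of dose selection for a later study. The primary comparison is high dose against placebo. A column that mixes the two doses 3:1 does not let a reader of these tables set the high-dose adverse-event rate beside the high-dose efficacy result, or see whether an event is more frequent at one dose.

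The cutoff adds to this. The non-serious table lists only events above X, so the choice of denominator affects which events are listed as well as the percentages. X is left until the tables are prepared. Protocol 6.4 allows all roles to be unblinded after final database lock, so nothing in the text prevents X from being chosen with the results in view.

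**Working it through.** **Inputs.** The total of 56, the 3:1:3 ratio and the arm sizes come from SAP 1.4. The value of X is not given, so whole-number values from 1% to 20% are assumed. Three further assumptions apply: every randomized patient is dosed, X is applied to each column separately, and the placebo column does not by itself bring the event above X.

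**Arm sizes reproduced.** 56 × 3/7 = 24 high dose, 56 × 1/7 = 8 low dose, 56 × 3/7 = 24 placebo. These match the plan. The pooled LYS006 column has 24 + 8 = 32 patients.

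**Dilution.** Pooled rate = (24 × high rate + 8 × low rate)/32 = 0.75 × high rate + 0.25 × low rate.

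- High dose only: 6/24 = 25.0% becomes 6/32 = 18.8%; 3/24 = 12.5% becomes 3/32 = 9.4%.
- Low dose only: 1/8 = 12.5% becomes 1/32 = 3.1%; 2/8 = 25.0% becomes 2/32 = 6.3%.
- Graded: 25% high and 12.5% low give 0.75 × 25 + 0.25 × 12.5 = 21.9%.

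**Listing in the non-serious table.** For each X, find the smallest count k with k/n above X%, for n = 24, 8 and 32. An event confined to one dose is lost by pooling when its count reaches the threshold for its own arm but not the threshold for 32.

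| Assumed X (%) | High-dose-only counts lost | Low-dose-only counts lost |
|---|---|---|
| 1, 2, 3 | none | none |
| 4 | 1 | 1 |
| 5, 6 | none | 1 |
| 7, 8 | 2 | 1, 2 |
| 9 | none | 1, 2 |
| 10, 12 | 3 | 1, 2, 3 |
| 15 | 4 | 2, 3, 4 |
| 20 | 5, 6 | 2 to 6 |

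At X = 5%, for example, 1/24 (4.2%) is unlisted either way, and 2/24 (8.3%) is still listed when pooled (2/32 = 6.3%).

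**Chance of listing.** Take a true high-dose rate of 12.5% with no low-dose events, and a binomial count in 24 patients:

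- X = 5%: at least 2 events are needed either way, so 82% by group and 82% pooled.
- X = 7%: at least 2 by group (82%), at least 3 pooled (59%).
- X = 10%: at least 3 by group (59%), at least 4 pooled (35%).

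**The case against.** The strongest reply is that the pooling touches only two tables made to meet registry requirements. The secondary endpoint, number and severity of adverse events, is served by other outputs in SAP 7.2, where adverse-event information stays by treatment group and subject. The sponsor's own dose decision does not rest on the registry tables. This stands, and it limits the point to those two tables.

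The reply is also right on several stronger readings that a reader might infer.

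- *Dose-related harm is hidden from the study.* It is not, because the by-group displays remain.
- *Serious events could disappear.* The cutoff is attached only to the non-serious table. For serious events the effect is dilution and lost dose attribution.
- *Pooling necessarily removes high-dose events.* At assumed X of 1, 2, 3, 5, 6 or 9% it removes none.
- *These tables are the only public safety record.* Protocol 12.3 provides for publication and/or posting and does not say so.
- *The high-dose risk estimate is biased.* The column is defined as all LYS006 and does not claim to estimate high-dose risk. The loss is of dose information.
- *The main event tables are pooled too, because the SAP describes them as by treatment.* Protocol 11.5.1 uses that phrase and by treatment group interchangeably, for example for vital signs, and the SAP adds the dose-pooling gloss only for the disclosure tables. Aligning the wording would be an editorial change.

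One might add that registry rules could constrain X. The documents do not show this, so how free the team is to choose X cannot be judged from them. None of this removes the conflict with Protocol 11.5.1, which is worded for all safety tables.

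**Conclusion.** The point holds for the two disclosure tables. The SAP's pooling rule contradicts the protocol's by-group rule without a visible reason. The contradiction and the loss of dose attribution are certain from the text and the arm sizes: a single-dose event shows at three quarters (high) or one quarter (low) of its arm rate.

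Omission of an event is possible but not certain. It concerns only the non-serious table and depends on X, on the event being concentrated in one dose, and on the column-by-column reading of the cutoff. The low-dose arm is the more exposed: a single low-dose event, 12.5% of that arm, is lost at every X examined from 4% to 12%. One patient in 8 is, however, little evidence of a dose effect. The counts assume a safety set of all 56 patients and would shift slightly if some were not dosed.

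The study's efficacy decision is not affected. The change is still worth making, because it removes a contradiction with the protocol and alters what the two tables show.

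**What to change.** In the disclosure part of SAP 7.2, replace the pooling sentence with a rule that both tables are summarized by treatment group (LYS006 high dose, LYS006 low dose, placebo), with an all-LYS006 column allowed in addition. State that a non-serious event is listed if its incidence exceeds X% in any single group. Give X a value in the SAP before unblinding. If the sponsor prefers to keep the pooled presentation, the SAP should record it as a departure from Protocol 11.5.1 and give the reason.

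The cost is SAP wording and one extra column in each of two tables, or two if the pooled column is kept. No new data are needed. The downside is a somewhat longer non-serious table, because one event in 8 low-dose patients already gives 12.5%, and low-dose percentages that rest on very small counts. Showing counts beside percentages makes that plain.
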